8.6.3 Other covariates, including confounders, effect modifiers and other variables

The following covariates will be reported as part of patient and treatment characterisation for each specific individual JAKi ingredient.

- Age at index date will be calculated. Age will be presented as a mean/median age as well as proportion of patient stratified within age groups (0-3, 4-12, 13-18, 19-40, 41-60, >60).
- Sex (male/female)
- Pre-specified indicated condition for JAKi, defined by condition recorded before index date (yes/no for each indication). Indications of JAKi will be defined by any records of the above-mentioned prespecified conditions before the first exposure of specific individual JAKi ingredient. Multiple indications are allowed. Preliminary code lists for the pre-defined indications are provided in Appendix I.
 - Atopic dermatitis
 - Juvenile idiopathic arthritis
 - o Inflammatory bowel disease
 - o Alopecia areata
 - Axial spondyloarthritis
 - Psoriatic arthritis
 - Rheumatoid arthritis
 - Unknown indication (defined as none of the predefined indications were found)
- Time from first indication to first JAKi initiation, estimated separately for each pre-specified indication (more than one per patient is possible) and presented in months
- Duration of index JAKi treatment era (months)
- Prior use of other JAKi (yes/no)

In addition, a large-scale characterisation for identifying potentially missing diagnosis codes from prespecified lists will be performed.

The following covariates will be used for the stratification in patient characterisation.

- Pre-defined indication

The study covariates are described conceptually, and the context or rationale for the choices are provided in this section. The operational definition of the covariates is described in the **Table 5**.

Author(s): [name], [name]

Version: V3.0

Dissemination level: Public

Table 5. Operational definitions of covariates.

Characteristic	Details	Type of variable	Assessment window	Care Settings ¹	Code Type	Diagnosis Position ²	Applied to study populations	Measurement characteristics/validation	Source for algorithm
Age	Age at index date in years	Numeric, continuous	[0,0]	OP	N/A	N/A	individual JAKi ingredient	N/A	N/A
Sex	Biological sex as recorded	Binary, count	[0,0]	OP	N/A	N/A	individual JAKi ingredient	N/A	N/A

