Indication	Diagnosis of pre-defined condition considered as possible indication for JAKi, including atopic dermatitis, juvenile idiopathic arthritis, inflammatory intestinal disease, alopecia areata, axial spondyloarthritis, psoriatic arthritis, rheumatoid arthritis and unknown indication	Binary, count	[-Inf, -1]	ОР	SNO MED	N/A	individual JAKi ingredient	N/A	N/A
Time from first diagnosis of indication to JAKi initiation	Time from first possible indication for JAKi to first exposure of each individual JAKi ingredient	Numeric, continuous	[-Inf, 0]	OP	N/A	N/A	individual JAKi ingredient	N/A	N/A
Treatment duration	Duration of JAKi used	Numeric, continuous	[0, end of index drug era]	OP	N/A	N/A	individual JAKi ingredient	N/A	N/A

¹IP = inpatient, OP = outpatient, ED = emergency department, OT = other, n/a = not applicable

² Specify whether a diagnosis code is required to be in the primary position (main reason for encounter)

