JAKi initiators will be characterized in terms of age, sex, and time from first diagnosis of prespecified indication to first JAKi exposure. Treatment characterisation will include indication and duration of treatment. Reporting on patient-level characterisation will be stratified by each individual JAKi ingredient and indication.

Duration of treatment

P3-C1-001 Stud	dy Protocol
----------------	-------------

Version: V3.0

Dissemination level: Public

Drug eras will be defined as follows: exposure starts at date of the first prescription, e.g., the index date the person entered the cohort. For each prescription, the estimated duration of use will be retrieved from the drug exposure table in the CDM, using the start and end date of the exposure. Subsequent prescriptions will be combined into continuous exposed episodes (drug eras) if the distance in days between end of the first exposure and start of the second exposure is ≤ 90 days. For the included individuals, the duration of JAKi use will be calculated by sum of duration of first drug eras during the study period. Treatment duration will be summarised providing the minimum, p25, median, p75, and maximum duration.

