11. LIMITATIONS OF THE RESEARCH METHODS

The study will be informed by routinely collected health care data and so data quality issues must be considered. In particular, a recording of a prescription or dispensation does not mean that the patient actually took the drug. In addition, assumptions around the duration of drug use will be unavoidable.

The actual reason for prescription of the drug is not recorded in any of the databases. We will assess indication via a proxy based on pre-defined conditions recorded on the date of therapy initiation. Therefore, recording of potential indication may be incomplete. In addition, the completeness of recordings of co-morbidities used for patient characterisation may variate across databases.

In IQVIA DA Germany, the observation period of the patients in these databases is calculated based on the last visit, observation or interaction of the patient with the health care system. This methodology impacts the individuals considered "at risk" for the different medicines of interest of the study (i.e., the individuals included in the denominator populations) during the latest months of available data from the latest data lock, where healthy and/or non-frequent users of the health care system will not be considered active. Consequently, the denominators that will be used to calculate the incident use of drugs in the population may present an artefactual decrease whilst the incident users will remain. The presence of these artefacts will be considered when interpreting the results.

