arthritis	558	Rheumatoid arthritis (RA) disease activity, low (RA)	ation
Rheumatoid	1176	Dharmataid anthritis disease acronity level [DARID3]	observ
arthritis	038	Rheumatoid arthritis disease severity level [RAPID3]	ation
Rheumatoid	2561	Dhawaataid baar diaasa	conditi
arthritis	97	Rheumatoid lung disease	on
Rheumatoid	8109	Faltida a vadrana	conditi
arthritis	7	Felty's syndrome	on
Rheumatoid	8080	Di como de se	conditi
arthritis	9	Rheumatoid arthritis	on
Rheumatoid	4048	Di dia di di di di di	measur
arthritis	1048	Disease activity score in rheumatoid arthritis	ement
Rheumatoid	4048		measur
arthritis	1959	Disease activity score in rheumatoid arthritis using C-reactive protein	ement
Rheumatoid	4048	Di dia contrata di dia	measur
arthritis	2839	Disease activity score 28 joint in rheumatoid arthritis	ement
Rheumatoid	4028	DW 14 WHI WILL OF	Conditi
arthritis	118	Diffuse interstitial rheumatoid disease of lung	on
Rheumatoid	3654	Onlindling of figures of hillstockling do do to the second district	Conditi
arthritis	567	Spindling of fingers of bilateral hands due to rheumatoid arthritis	on
Alopecia	4300	Circums with a distance is a second of seconds	Conditi
areata	910	Circumscribed alopecia areata of scalp	on
Alopecia	4300	Circumperihad alamasis areats of avalanhas/avahraya	Conditi
areata	911	Circumscribed alopecia areata of eyelashes/eyebrows	on
Alopecia	4300	Circumsonib ad alamasia areata of based area	Conditi
areata	912	Circumscribed alopecia areata of beard area	on
Alopecia	4300	Circumsonib ad alamasia areata of limba	Conditi
areata	913	Circumscribed alopecia areata of limbs	on
Alopecia	4300	Circumscribed alopecia areata of trunk	Conditi
areata	914	Circumscribed alopeda areata or trunk	on
Alopecia	4263	Diffuse alopecia areata	Conditi
areata	194	Diffuse alopeda afeata	on
Alopecia	1419	Alopecia areata	Conditi
areata	33	Alopedia aleata	on
Alopecia	4300	Concentrio aleneoia areata	Conditi
areata	094	Concentric alopecia areata	on
Alopecia	4312	Alopecia universalis	Conditi
areata	756	Alopeola utiliversalis	on
Alopecia	4239	Ophiagic	Conditi
areata	312	Ophiasis	on
Alopecia	4056	Alanacia tatalia	Conditi
areata	343	Alopecia totalis	on
Alopecia	3671	Alopecia, psychomotor epilepsy, periodontal pyorrhea, intellectual disability	Conditi
areata	5349	syndrome	on

Author(s): [name], [name]

Version: V3.0

Alopecia	3720	Alopecia antibody deficiency	Conditi
areata	3833	.,	on
Atopic dermatitis	1340 257	Exacerbation of atopic dermatitis	Conditi on

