Atopic dermatitis	4033 770	Constitutional fingertip eczema	Conditi
Atopic	3711	Exacerbation of constitutional dermatitis due to occupation	Conditi
dermatitis Atopic	0589 4223	'	on Conditi
dermatitis	498	Chronic vesicular eczema of hands and feet	on
Atopic dermatitis	4223 477	Vesicular hand eczema	Conditi
Atopic	4080	Constitutional discoid hand eczema	Conditi
dermatitis Atopic	931 4066		on Conditi
dermatitis	727	Besnier's prurigo	on
Atopic dermatitis	4031 634	Constitutional eczema of foot	Conditi
Atopic dermatitis	4309 200	Allergic inhalant dermatitis	Conditi
Atopic	4031	Chronic podopompholyx	Conditi
dermatitis Atopic	017 3720	Acute vesicular eczema of foot	on Conditi
dermatitis Atopic	3896 4297		on Conditi
dermatitis	495	Chronic constitutional eczema	on
Atopic dermatitis	4031 016	Constitutional eczema of hand	Conditi
Atopic dermatitis	4033 769	Apron pattern of vesicular eczema of hands	Conditi
Atopic dermatitis	4221 832	Acute-on-chronic vesicular eczema of hands	Conditi
Atopic dermatitis	4033 672	Constitutional eczema of hands and feet	Conditi
Atopic	4221	Acute vesicular eczema of hand	on Conditi
dermatitis Atopic	829 4297		on Conditi
dermatitis	494	Acute constitutional eczema	on Conditi
Atopic dermatitis	4290 745	Chronic relapsing vesiculosquamous hand eczema	on
Atopic dermatitis	3654 806	Eczema coxsackium	Conditi on
Atopic dermatitis	4067 178	Podopompholyx	Conditi on
Atopic dermatitis	4223 639	Chronic vesicular eczema of hands	Conditi
Axial spondyloarthriti s	6073 98	Axial spondyloarthritis with peripheral joint involvement	Conditi
Axial spondyloarthriti s	3701 7494	Non-radiographic axial spondyloarthritis	Conditi

Author(s): [name], [name]

Version: V3.0

Axial spondyloarthriti s	3671 6891	Axial spondyloarthritis	Conditi on
Axial spondyloarthriti s	4370 82	Ankylosing spondylitis	Conditi on
Axial spondyloarthriti s	1340 249	Exacerbation of ankylosing spondylitis	Conditi on
Axial spondyloarthriti s	4035 741	Ankylosing spondylitis with multisystem involvement	Conditi
Axial spondyloarthriti s	3720 3959	Ankylosing spondylitis co-occurrent with anterior uveitis	Conditi
Axial spondyloarthriti s	4079 735	Juvenile spondyloarthropathy	Conditi
Axial spondyloarthriti s	4035 614	Ankylosing spondylitis with organ / system involvement	Conditi
Axial spondyloarthriti s	4083 681	Juvenile ankylosing spondylitis	Conditi on
Juvenile idiopathic arthritis	1340 385	Exacerbation of juvenile idiopathic arthritis	Conditi on

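### By-indication results rest on overlapping strata defined by any earlier record, so they can include users treated for another condition, and nothing planned shows how many

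*Protocol*

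**What the plan says.** Section 8.6.3 defines the variable: "Indications of JAKi will be defined by any records of the above-mentioned prespecified conditions before the first exposure of specific individual JAKi ingredient". It adds: "Multiple indications are allowed". Table 5 describes the variable as "Diagnosis of pre-defined condition considered as possible indication for JAKi" and gives the window [-Inf, -1]; Figure 2 shows the same window. There is no rule on recency, repeat records or precedence between conditions.

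The variable is then used to stratify. Section 8.8.2: "Reporting on patient-level characterisation will be stratified by each individual JAKi ingredient and indication". Section 14 lists what is shown for each indication: age, time from first diagnosis, duration of the first drug era, and the percentage with earlier use of another JAKi. No count of indication combinations and no single-indication stratum is listed, and item 10.8 of the ENCePP checklist does not claim any sensitivity analysis.

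Section 11 concedes: "The actual reason for prescription of the drug is not recorded in any of the databases". It continues: "We will assess indication via a proxy based on pre-defined conditions recorded on the date of therapy initiation". The consequence it draws is that recording may be incomplete.

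**The concern.** A JAKi user who is treated for one listed condition and has a single old code for another is analysed as a user in both. In the second stratum that user's age and treatment duration belong to a different treated population, and the time from first diagnosis runs from a code that may have nothing to do with the prescription.

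The stakes come from section 6. The study is to inform the feasibility of later safety studies, evidence is thin mainly outside rheumatoid arthritis, and use in the newer indications has been uncommon. A given number of stray users distorts a small stratum more than a large one, so both the counts and the profiles are least reliable where they will be relied on most.

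The code lists can add to this. Table s2 places "Eczema coxsackium" under atopic dermatitis, and under alopecia areata a syndrome that begins "Alopecia, psychomotor epilepsy, periodontal pyorrhea, intellectual disability". By name, neither is the condition it is filed under.

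**Working it through.** **No stated figure to reproduce.** The plan gives no distribution of users by indication, no overlap rate and no sample-size calculation. What follows shows how the definition behaves; it does not estimate the error.

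**Inputs, all assumed.**
- t: the share of an ingredient's users truly treated for the indication, 2% to 10%.
- q: the probability that a user treated for something else has any earlier record of that condition, 1% to 10%.
- Every true user is taken to have a code.

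**Formulas.** For N users:
- stratum size = N·t + N·(1−t)·q
- share treated for something else = (1−t)·q / [t + (1−t)·q], which does not depend on N

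**Worked case.** Take N = 2500, the FinOMOP-HILMO feasibility count in section 8.7 (all JAKi together, so only a scale), with t = 5% and q = 3%. True users: 2500 × 0.05 = 125. Stray users: 2500 × 0.95 × 0.03 = 71.25. Stratum: 196.25. Share treated for something else: 71.25 / 196.25 = 36.3%.

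**Grid of that share.**

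| t | q = 1% | q = 3% | q = 5% | q = 10% |
|---|---|---|---|---|
| 2% | 32.9% | 59.5% | 71.0% | 83.1% |
| 5% | 16.0% | 36.3% | 48.7% | 65.5% |
| 10% | 8.3% | 21.3% | 31.0% | 47.4% |

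Half the stratum is misassigned once q = t/(1−t), which is 2.0%, 5.3% and 11.1% for t = 2%, 5% and 10%. The range of 8% to 83% reflects only the assumptions. What holds throughout is that, for a given q, the share rises as t falls.

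**How much would be rheumatoid arthritis.** Let r be the rheumatoid arthritis share of an ingredient's users, with the same q for everyone not truly in the stratum. The part of the stray users treated for rheumatoid arthritis is r/(1−t). At t = 5%, r = 70% gives 0.70/0.95 = 74%, and r = 10% gives 0.10/0.95 = 11%. The documents do not give r for any ingredient.

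**Incomplete coding does not cancel this.** If only a fraction s of true users have a code, the share becomes (1−t)·q / [s·t + (1−t)·q], which is larger for s below 1. Under-recording may offset the inflation of the count, but it worsens the mix.

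**Windows side by side.** Section 8.6.3, Table 5 and Figure 2 use all days up to the day before index. Section 11 says the day of initiation. These windows have no day in common, so section 11 describes a different variable from the one to be analysed.

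**The case against.** The design is open about what it does. It speaks of possible indications, permits several, estimates time from diagnosis separately for each, and calls the measure a proxy because the reason for prescribing is not recorded. In a descriptive study, any-record strata are a legitimate choice, and some patients really do have two indications. This stands, and it is why the planned strata should remain.

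The code lists are labelled preliminary. Section 10 plans a relevance review by two clinical epidemiologists and a diagnostic tool to help judge whether more than one definition is needed. This also stands: pruning Table s2 fits within a step already planned. However, the stated aim of the large-scale characterisation is to find missing codes, and section 10 has the diagnostic tool look for omitted ones, so the relevance review is where wrongly included concepts must be caught.

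An exactly-one stratum has its own bias. It drops patients with two true indications and favours short records, since a longer history gives more chance of a second code. It also leaves in a user whose true indication is unrecorded but who has an old code for something else. This rules it out as a replacement for the planned strata, but not as a companion to them.

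A reader might infer three stronger things, none of which the documents support:
- *That the stray users are mainly rheumatoid arthritis patients.* Section 6 makes this plausible for the class, but the tables are per ingredient and no ingredient's mix is given. For an ingredient used mostly for another condition, the flow could run the other way.
- *That a particular percentage of a stratum is wrong.* Every input to such a figure is assumed.
- *That the look-back is lifelong.* It is limited to database history: FinOMOP-HILMO from 2011, IPCI from 2006, the VID instance 2018 to 2021. In NLHR the primary-care diagnosis source is described as coming in a later release. The route for stray codes therefore differs by database.

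**Conclusion.** The concern holds as a limitation of the by-indication results that the plan neither measures nor states. Followed as written, the definition counts a user in every stratum for which any earlier code exists. It reports the by-indication profiles only in those strata and provides nothing from which a reader could see the overlap. The distortion is proportionally largest for uncommon indications.

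Its size, and the part due to rheumatoid arthritis, cannot be derived from the documents and will vary by ingredient and database; the grid is illustrative only. Separately, and without any assumption, section 11 contradicts section 8.6.3 and Table 5 on the time window and omits over-inclusion as a limitation.

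This is a worthwhile and inexpensive improvement. It does not invalidate the study.

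**What to change.** 1. Keep the any-record strata as planned.
2. For each ingredient and database, add a count of indication combinations: exactly one (by condition), two or more, none.
3. Report age, time from first diagnosis and treatment duration in the exactly-one strata beside the planned ones, labelled as a sensitivity analysis and not as a replacement.
4. At the relevance review in section 10, before the code is run, remove Table s2 concepts that are not the named condition; the two named above are examples to check.
5. Reconcile section 11 with section 8.6.3, Table 5 and Figure 2 on the window, and state over-inclusion as a limitation next to incompleteness.

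No new data are needed. The cost is one derived variable, a combination count, a second set of columns and some text edits. The downside is more cells below 5, mainly in VID (feasibility count 600) and IPCI (700). The exactly-one strata will exclude true dual-indication patients and will not correct cases where the true indication was never recorded; the report should say so.

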The patient level cohort study will include all JAKi new users from the 1st January 2017 until the most recent data lock of their respective databases, with at least 365 days of data visibility.

Variables

Drugs of interest: JAKi: abrocitinib, filgotinib, baricitinib, upadacitinib, tofacitinib

P3-0	1-00	11 Sti	ıdv Pr	otocol

Version: V3.0

Dissemination level: Public

Indications: atopic dermatitis, juvenile idiopathic arthritis, inflammatory bowel disease, alopecia areata, axial spondyloarthritis, psoriatic arthritis, rheumatoid arthritis, unknown indication

Patient characteristics: age, sex, time from first diagnosis of indication to JAKi therapy initiation

Treatment characteristics: duration of index treatment drug era

Stratification: ingredient (specific JAKi), and indication

Data source

- 1. FinOMOP-HILMO (Finland)
- 2. IPCI (The Netherlands)
- 3. IQVIA DA Germany (Germany)
- 4. NLHR (Norway)
- 5. VID (Spain)

Sample size

No sample size has been calculated for this study. Based on the preliminary feasibility assessment, expected number of subjects to be involved in each data source would be approximately between 600 and 7900.

Statistical analysis

Incidence of new JAKi use, overall and for each individual JAKi ingredient, will be calculated yearly as the number of new users per 100,000 person-years of the population at risk of getting exposed during the period for each calendar year, with 95% Poisson exact confidence intervals. Patient characterisation on new JAKi users will be done based on age, sex and indication for each JAKi ingredient, over all indications and stratified by indication. Patient characterisation on time from first diagnosis of indication to first JAKi initiation, and treatment duration of the first drug era will be reported for each JAKi ingredient stratified by indication. Time from first diagnosis of indication to treatment initiation and treatment duration will be summarised, providing the minimum, p25, median, p75, and maximum duration.

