7. RESEARCH QUESTION AND OBJECTIVES

Table 1. Primary and secondary research questions and objective.

A. Objective 1. Population-level drug utilisation

Objective 1:	To estimate the incidence of new JAKi use, overall and for each individual JAKi ingredient	
Hypothesis:	Not applicable	
Population (mention key inclusion- exclusion criteria):	The study includes all people available in the databases with at least 365 days of data visibility.	
Exposure:	Not applicable	
Comparator:	Not applicable	
Outcome:	JAKi (abrocitinib, filgotinib, baricitinib, upadacitinib, tofacitinib)	
Time (when follow up begins and ends):	From 1 st January 2017 until the most recent data lock for each included database.	
Setting:	Data will be collected from primary care and secondary care outpatient setting with the following databases:	
	- FinOMOP-HILMO (primary care, secondary care outpatient)	
	- IPCI (primary care)	
	- IQVIA DA Germany (primary care)	
	- NLHR (primary care, secondary care outpatient)	
	- VID (primary care, secondary care outpatient)	
Main measure of effect:	Annual incidence rates of JAKi use, for the entire class pooled together and for each JAKi ingredient	

B. Objectives 2. Patient-level characterisation and drug utilisation studies

Objective 2:	To characterise new JAKi users and treatment, overall and stratified by ingredient and indication	
Hypothesis:	Not applicable	
Population (mention key inclusion- exclusion criteria):	The study includes all patients available in the databases initiating JAKi therapy, with at least 365 days of data visibility before therapy initiation	
Exposure:	JAKi (abrocitinib, filgotinib, baricitinib, upadacitinib, tofacitinib)	
Comparator:	Not available	
Outcome:	Not available	
Time (when follow up begins and ends):	For treatment characterisation: from each JAKi therapy initiation until the discontinuation of index drug	
Setting:	Data will be collected from primary care and secondary care outpatient setting with the following databases: - FinOMOP-HILMO (primary care, secondary care outpatient)	

DARWIN M	P3-C1-001 Study Protocol	
○EU/V	Author(s): [name], [name]	Version: V3.0
,		Dissemination level: Public

	 IPCI (primary care) IQVIA DA Germany (primary care) NLHR (primary care, secondary care outpatient) VID (primary care, secondary care outpatient)

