The THL HILMO database covers both public and private, primary and specialised inpatient and outpatient health care encounters in Finland starting from 2011. The entire public sector and private inpatient encounters have been included since 2011, while private outpatient encounters, including occupational care, are included since 2020. The main content of the THL CDM is The Finnish Care Register for Health Care (fi:Hoitoilmoitusrekisteri, HILMO). It is a continuation of the former Hospital Discharge Register, which originally gathered data on patients discharged from hospitals. The Care Register has comprehensive data on the use of services and service users from Finnish public inpatient and outpatient primary and specialised care nationwide. Since 1998 the register has covered both public outpatient and inpatient specialised care and private inpatient care (TerveysHilmo). From 2011 the register has covered public primary care (AvoHilmo). From 2020 the register has covered private outpatient care and occupational care. In addition, the CDM also contains the vaccination data from the Finnish National Vaccination Register, and positive COVID-19 test results from the Finnish National Infectious Diseases Register, which is maintained by THL. The CDM is currently produced from the above-mentioned, and limited to observation periods commencing after 1.1.2011. The National Population registry is also used as a source for the CDM database. The National Population registry data forms the basis for forming the patient population. This ensures up-to-date location (municipality of residence) of patients as well as complete death occurrences (although not the cause of death). Using the complete population as a basis for the person table also serves to facilitate calculations on a population level, e.g. incidence rates. The current CDM population comprises all persons having been alive and residing in Finland since the beginning of 2011.

Integrated Primary Care Information [IPCI] (The Netherlands)

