The Valencia Health System Integrated Dataset (VID) is a set of multiple, public, population-wide electronic databases for the Valencia Region, the fourth most populated Spanish region, with about 5 million inhabitants and an annual birth cohort of 48 000 newborns, representing 10.7% of the Spanish population and around 1% of the European population. The VID provides exhaustive longitudinal information including sociodemographic and administrative data (sex, age, nationality, etc.), clinical (diagnoses, procedures, diagnostic tests, imaging, etc.), pharmaceutical (prescription, dispensing) and healthcare utilisation data from hospital care, emergency departments, specialised care (including mental and obstetrics care), primary care and other public health services. It also includes a set of associated population databases and registries of significant care areas such as cancer, rare diseases, vaccines, congenital anomalies, microbiology (including COVID-19 test results registry) and others, and also public health databases from the population screening programmes. All the information in the VID databases can be linked at the individual level through a single personal identification code. The databases were initiated at different moments in time, but all in all the VID provides comprehensive individual-level data fed by all the databases from 2008 to date. The OMOP instance has been created using CONSIGN project data, where 1.96 million of females in fertile age are studied from start of 2018 to end of 2021.

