8.3 Study period

The study period starts from 1st January 2017 until the most recent data lock for each included database (see **Table 3**).

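### Time from first diagnosis to JAKi start is cut off where each database's records begin, to a depth that differs by database and is not disclosed; in VID it may be close to uninformative

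*Protocol*

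**What the plan says.** Table 5 in section 8.6.3 defines the variable as "Time from first possible indication for JAKi to first exposure of each individual JAKi ingredient", with a window open to minus infinity. The same section accepts any earlier record as the indication: "Indications of JAKi will be defined by any records of the above-mentioned prespecified conditions before the first exposure of specific individual JAKi ingredient". The diagnosis need not be new, and no common look-back is set. The only history condition, in Table 1 of section 7, is inclusion "with at least 365 days of data visibility before therapy initiation"; sections 8.4 and 8.5 repeat the 365 days.

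The abstract fixes the summary: "Time from first diagnosis of indication to treatment initiation and treatment duration will be summarised", by minimum, quartiles and maximum. Section 7 lists the time among the main measures of Objective 2, and section 14 promises it for each indication.

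On available history, section 8.2 describes the VID OMOP instance as one where "1.96 million of females in fertile age are studied from start of 2018 to end of 2021", and Table 3 gives its lock as 2022-01-01. The FinOMOP-HILMO data are "limited to observation periods commencing after 1.1.2011". IPCI records run from 2006 and IQVIA DA Germany from 1992. No start is given for the NLHR extract. Section 8.3 adds: "The study period starts from 1st January 2017 until the most recent data lock for each included database".

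**The concern.** An open-ended window reaches back only as far as the person's data. In rheumatoid arthritis, inflammatory bowel disease or atopic dermatitis, many patients will have been diagnosed years before a JAKi. If that diagnosis predates the record, the first code found is merely the first one captured, and the computed time is shorter than the true one. Strictly, it is a censored value, yet the plan mixes it with complete values and takes ordinary quantiles.

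The depth of the cut differs by database, so results shown database by database can differ because of record length alone. The study is meant to inform the feasibility of later safety studies. A disease-duration figure that is too short, with no warning attached, would carry into their design. Section 11 warns that indication recording may be incomplete, but not that the first recorded date may postdate the diagnosis or that look-back is unequal.

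**Working it through.** The protocol gives no expected value for this variable, so there is no figure to reproduce.

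**Step 1: calendar ceiling.** Longest observable time = index date minus first date of data, in months of 30.4375 days. Earliest index = the later of 1 January 2017 and data start + 365 days. Start dates are from section 8.2 (1 January of the stated year), locks from Table 3.

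| Database | Data from | Lock | Ceiling at earliest index | Ceiling at lock |
|---|---|---|---|---|
| VID instance | 2018 | 2022-01-01 | 12.0 | 48.0 |
| FinOMOP-HILMO | 2011 | 2024-04-16 | 72.0 | 159.5 |
| IPCI | 2006 | 2024-04-30 | 132.0 | 219.9 |
| IQVIA DA Germany | 1992 | 2023-09-30 | 300.0 | 380.9 |
| NLHR | not stated | 2024-06-30 | not computable | not computable |

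These are upper limits. A person who entered later has less history, down to 12 months.

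**Step 2: effect on the summary.** The documents give no disease durations, so the following are assumptions: true time D is exponential with median M; look-back L is uniform between the two ceilings a and b; a patient diagnosed earlier is coded at entry. The reported value is min(D, L), and the proportion exceeding t is

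2^(−t/M) × P(L > t), with P(L > t) = 1 for t ≤ a and (b − t)/(b − a) for a < t < b.

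The reported median is the t at which this equals 0.50; p75 is where it equals 0.25. The share truncated is M/[ln 2 × (b − a)] × [2^(−a/M) − 2^(−b/M)].

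VID, M = 60:
- Median: 2^(−24.2/60) × (48 − 24.2)/36 = 0.756 × 0.661 = 0.50, so 24.2 months.
- Share truncated: 60/(0.693 × 36) × (0.871 − 0.574) = 0.71.

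FinOMOP-HILMO, M = 60:
- The median of 60 lies below a = 72, so it is unaffected.
- p75: 2^(−94.4/60) × (159.5 − 94.4)/87.5 = 0.336 × 0.744 = 0.25, so 94 months against a true 2 × 60 = 120.

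| True median | VID: reported median | VID: truncated | FinOMOP: reported median | FinOMOP: truncated |
|---|---|---|---|---|
| 36 | 21 | 57% | 36 | 12% |
| 60 | 24 | 71% | 60 | 27% |
| 96 | 26 | 81% | 81 | 44% |
| 120 | 27 | 84% | 87 | 52% |

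In VID, more than tripling the true median moves the reported one by six months. With full calendar history, the truncated shares at true medians of 60 and 120 are 14% and 37% in IPCI, and 2% and 14% in IQVIA DA Germany. The medians there are unaffected.

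**Step 3: sensitivity to the assumptions.** These runs let a previously diagnosed patient be first coded 0 to 6 months after data start.
- VID: true medians of 24, 60 and 120 are reported as about 16, 22 and 24 months.
- Individual look-back spread evenly from 12 months to the ceiling: truncated shares at true medians of 60 and 120 become 42% and 63% (FinOMOP-HILMO), 33% and 54% (IPCI), and 20% and 39% (IQVIA DA Germany). A true median of 60 is reported as about 40, 44 and 50 months respectively.
- VID with history from 2008 loaded and index dates from 2017: the ceiling becomes 108 to 168 months, and true medians of 60 and 120 are reported as 60 and 109.

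**The case against.** The strongest reply is that the damage is concentrated in one small source. Section 8.7 expects 2500 + 700 + 7900 + 2600 + 600 = 14,300 users; VID supplies 600, about 4%, and IQVIA DA Germany 7900, about 55%. The 365 days are a floor, not the usual look-back. A reader might infer that the measure mostly reports record length throughout the study. The documents do not support that: calendar history at index is at least 6 years in FinOMOP-HILMO, 11 in IPCI and 25 in IQVIA DA Germany, and the FinOMOP-HILMO median is right at true medians of 36 to 60 months. This part of the reply stands.

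Two further inferences also go too far. The 48-month VID ceiling is not certain, because section 8.2 says the parent system holds data from 2008 and does not say whether earlier diagnoses were loaded. Nor do the documents say that a person's history in IPCI or IQVIA DA Germany begins at practice registration or first visit; section 11 explains only how IQVIA observation time is derived from the last contact.

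It is also fair that section 14 already describes the diagnosis as the first one identified, that the measure is descriptive, and that sections 8.8 and 8.9 plan separate results with no pooling. This lowers the stakes, but separate presentation does not tell the reader that the figures have different ceilings.

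**Conclusion.** The point holds in a limited form. The plan fixes an estimator that treats left-truncated times as complete, with a depth that varies by database, and does not disclose it.

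- **VID:** if nothing before 2018 is held, values are bounded at 12 to 48 months by index date, and the median says little about true disease duration.
- **FinOMOP-HILMO, IPCI and IQVIA DA Germany:** small to moderate with full calendar history, mainly on the upper quartile and maximum. It is larger if many patients have short individual histories, which the documents do not show.
- **NLHR:** cannot be assessed.

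The ceilings follow from dates in the protocol. The reported medians, quartiles and shares rest on assumed exponential durations and uniform look-back, and are illustrations rather than predictions. No hypothesis test or sample size is affected; the consequence is misreading a descriptive Objective 2 result. It should be corrected before results are produced.

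**What to change.** 1. Label the measure 'time since first recorded diagnosis' in the abstract, section 7, section 8.6.3 and Table 5, section 8.8.2 and section 14.
2. Report the distribution of prior observation time beside it for each database, and state where NLHR history begins.
3. Add a sensitivity summary, with the number affected. Either treat times as lower bounds when the first code falls early in the person's observation period (Kaplan-Meier quantiles looking back from index), or restrict to patients with a diagnosis-free run-in. This should not replace the main summary: a rule censoring any first code in the first 365 days would censor almost every VID patient starting in early 2019, including genuinely new diagnoses.
4. State whether diagnoses before 2018 are in the VID instance. If not, omit VID from this output or show it explicitly as bounded at 48 months.
5. Add unequal look-back to section 11.

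The cost is protocol wording, a few lines of code and slightly more output. No new data are needed. Some quantiles in the sensitivity summary may not be estimable.
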